9.3 Adverse Event Reporting Requirements

9.3.1 Investigator Reporting Requirements

All AEs, regardless of seriousness, severity, or presumed relationship to study therapy, must be recorded using medical terminology in the source document and in the eCRF. Whenever possible, diagnoses should be given when signs and symptoms are due to a common etiology (e.g., cough, runny nose, sneezing, sore throat, and head congestion should be reported as "upper respiratory infection"). Investigators must record in the eCRF their opinion concerning the relationship of the AE to study therapy. All measures required for AE management must be recorded in the source document and reported according to Endotronix instructions.

All events will be classified per Adverse Event definitions as documented in Appendix 14.7. Additionally, the date of the event, seriousness criteria and outcome should also be recorded.

Laboratory and clinical parameters will be followed to evaluate the safety and performance of the Cordella PA Sensor System; these include adverse event reporting and monitoring, routine clinical laboratory tests (hematology, biochemistry, and urinalysis), vital signs, review of concomitant medications and echocardiogram.

It is the responsibility of the investigators to inform their IRB/IEC of adverse events as required by their local IRB procedures.

Investigators must notify Endotronix (or designee) within 24 hours of discovering any Unanticipated Adverse Device Effects (UADE)/ Unanticipated Serious Adverse Device Effect (USADE). Investigators are required to submit a report of a UADE/ USADE to the reviewing IRB/ IEC as soon as possible, but in no event later than 10 working days after the investigator first learns of the event. UADEs/USADEs must be documented on the appropriate eCRF.

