Cardiovascular death includes death resulting from an acute myocardial infarction (MI), sudden cardiac death, death due to HF, death due to stroke, death due to CV procedures, death due to CV hemorrhage, and death due to other CV causes.

Non-cardiovascular death

Any death in which the primary cause of death is clearly related to another condition (e.g. trauma, cancer, suicide).

DEVICE / SYSTEM-RELATED COMPLICATION

A Device /system related complication is an adverse event that is, or is possibly, related to the system (wireless pressure sensor or external electronics) and at least one the following:

- is treated with invasive means (other than intramuscular medication or a right heart catheterization with a Swan-Ganz measurement which is used for diagnostic purposes)
- results in the death of the subject
- results in the explant of the device

HEART FAILURE (HF)

A HF Event includes hospitalization for HF and may include urgent, unscheduled outpatient office/practice or Emergency Department (ED) visits.

- A HF Hospitalization is defined as an event in which the patient is admitted to the hospital with a primary diagnosis of HF, the length of stay is at least 24 h, the patient exhibits new or worsening symptoms of HF on presentation, has objective evidence of new or worsening HF, and receives initiation or intensification of treatment specifically for HF.
- An Urgent HF Visit is defined as an event in which the patient has an urgent, unscheduled office/practice or ED visit for a primary diagnosis of HF but is not admitted to the hospital and exhibits new or worsening symptoms of HF on presentation, has objective evidence of new or worsening HF, and receives initiation or intensification of treatment specifically for HF. Note that changes to oral diuretic therapy do not qualify as initiation or intensification of treatment.

HEMOPTYSIS

Spitting up blood or blood-tinged sputum from the respiratory tract. Hemoptysis occurs when tiny blood vessels that line the lung airways are broken.

MYOCARDIAL INFARCTION (MI)

Peri-procedural MI (≤72 h after the index procedure)

- New ischemic symptoms (e.g. chest pain or shortness of breath), or new ischemic signs (e.g. ventricular arrhythmias, new or worsening HF, new ST-segment changes, hemodynamic instability, new pathological Q-waves in at least two contiguous leads, imaging evidence of new loss of viable myocardium or new wall motion abnormality).

AND

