3.3. Secondary Efficacy Endpoints

1. Incidence of HF Hospitalizations or all-cause mortality at 12 months
2. Number of HF Hospitalizations at 6 and 12 months post-implant compared to the number of HF Hospitalizations in the 6 and 12 months prior to implant
3. Comparison of the number of HF Hospitalizations or Emergency Department/ Hospital Outpatient IV diuretic visits of Cohort #1 and Cohort #2 + #3 at 6 and 12 months post implant
4. Change of N-terminal pro B-type Natriuretic Peptide (NT-proBNP) from Baseline through 6 and 12 months
5. Combined outcome of:
 - a. First and recurrent HF Hospitalizations
 - b. Heart failure Emergency Department/ Hospital Outpatient IV diuretic visits
 - c. all-cause mortalityat 6 months, added together with equal weighting into a total number of events.
6. Heart failure hospitalization or HF Emergency Department/ Hospital Outpatient IV diuretic visits at 6 and 12 month
7. Cardiac and all-cause mortality
8. Days Alive and Out of Hospital (DAOH)
9. Intravenous (IV) diuretic visits
10. Heart failure related Medication changes
11. Change in PAP:
 - a. From Baseline through 6 and 12 months in subjects with a baseline mPAP
 - i. above target range
 - ii. within or below target range
 - iii. Overall
 - b. Before and after 6-Minute Walk Test
12. Percentage of device success as documented by ability of the System to successfully transmit PAP data
13. Subject Outcome Measures, measured by Kansas City Cardiomyopathy Questionnaire (KCCQ)
14. Functional status improvement, as measured by NYHA and 6-Minute Walk Test
15. Health Economic Analysis (will be covered separately)

This document is confidential.

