7.1. Primary Efficacy Endpoint and Analysis

The primary efficacy endpoint is the 6 month incidence of HF related hospitalizations (HFH) or all-cause mortality.

The information on mortality will be used as collected on the CRF, AE page with AE outcome = 'Death' or Study completion page with primary reason for discontinuation = 'Death'.

The information on HF hospitalizations will be used as collected on the CRF, Hospitalization page, only hospitalizations due to heart failure and stay at least 24 h will be considered as HF related hospitalizations

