All events until day x, which would be exact 6 or 12 months (180 or 365 days respective) post-implant visit would be summarized.

All events happened between day x and implant visit, which is exact 6 or 12 months (-180 or -365 days respective) pre-implant visit. Analysis will be done based on mITT population, PP population, and Cohort #1 population. Prior to the date of cut-off for the main analysis, it will be confirmed, if analysis based on PP population will be required.

This document is confidential.

7.1.6. Comparison of the number of HF Hospitalizations or Emergency Department/ Hospital Outpatient IV diuretic visits of Cohort #1 and Cohort #2 + Cohort #3 at 6 and 12 month post implant

The rate of mortality and HF hospitalizations or HF emergency department/hospital outpatient IV diuretic visits in each cohort at 6 or 12 month is calculated as the total number of observed events in each cohort divided by the (total observed exposure time/180 or 365) in each cohort from implant visit through 6 months or 12 months.

The information on mortality will be used as collected on the CRF, AE page with AE outcome = 'Death' or Study completion page with primary reason for discontinuation = 'Death'. The information on HF hospitalizations will be used as collected on the CRF, Hospitalization page, emergency department/hospital outpatient IV diuretic visits will be used as collected on the CRF, AE page with AEs resulted in = 'Emergency Department (ED) visit'/'Hospitalization'/'Urgent, unscheduled outpatient office/ practice' for AE categorized as 'Heart failure'.

The Cohort #1 and Cohort #2 + Cohort #3 subjects will then be compared with respect to rate of events per unit time using poisson regression. The test will be based on each subject's total number of events, treatment arm, and exposure time, where a subject's exposure is the time to death, early study discontinuation or 6 or 12 months, whichever is smaller.

Let λ_1 be the rate of events per 6/12 month on the Cohort #1 and let λ_2 be the rate of events per 6/12 month on the Cohort #2 + Cohort #3. The null hypothesis is $H_0: \lambda_1 \leq \lambda_2$ and the alternative hypothesis is $H_1: \lambda_1 > \lambda_2$.

The poisson regression calculation provides a one-sided p-value for the null hypothesis that the rate in the Cohort #1 is less than or equal to the rate in the Cohort #2 + Cohort #3.. The resulting p-values will be seen as explanatory.

```
proc genmod data = xxx;  
    class trt;  

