	14.2.2.3.1	Comparison of HF hospitalizations or HF emergency department/hospital outpatient IV diuretic visits of Cohort #1 and Cohort #2 + Cohort #3 at 6 and 12 months post implant visit	Comparison population
	14.2.2.3.1a	SAS-Output: Comparison of HF hospitalizations or HF emergency department/hospital outpatient IV diuretic visits of Cohort #1 and Cohort #2 + Cohort #3 at 6 and 12 months post implant visit	Comparison population
	14.2.2.3.2	Comparison of HF hospitalizations or HF emergency department/hospital outpatient IV diuretic visits of Cohort #1 and Cohort #2 + Cohort #3 at 6 and 12 months post implant visit, stratified by sex	Comparison population
	14.2.2.3.2a	SAS-Output: Comparison of HF hospitalizations or HF emergency department/hospital outpatient IV diuretic visits of Cohort #1 and Cohort #2 + Cohort #3 at 6 and 12 months post implant visit, stratified by sex	Comparison population
	14.2.2.3.3	Comparison of HF hospitalizations or HF emergency department/hospital outpatient IV diuretic visits of Cohort #1 and Cohort #2 + Cohort #3 at 6 and 12 months post implant visit, stratified by heart failure ejection fraction	Comparison population
	14.2.2.3.3a	SAS-Output: Comparison of HF hospitalizations or HF emergency department/hospital outpatient IV diuretic visits of Cohort #1 and Cohort #2 + Cohort #3 at 6 and 12 months post implant visit, stratified by heart failure ejection fraction	Comparison population
	14.2.2.3.4	Comparison of HF hospitalizations or HF emergency department/hospital outpatient IV diuretic visits of Cohort #1 and Cohort #2 + Cohort #3 at 6 and 12 months post implant visit from CEC adjudication results	Comparison population
	14.2.2.3.4a	SAS-Output: Comparison of HF hospitalizations or HF emergency department/hospital outpatient IV diuretic visits of Cohort #1 and Cohort #2 + Cohort #3 at 6 and 12 months post implant visit from CEC adjudication results	Comparison population
	14.2.2.3.5	Comparison of HF hospitalizations or HF emergency department/hospital outpatient IV diuretic visits of Cohort #1 and Cohort #2 + Cohort #3 at 6 and 12 months post implant visit from CEC adjudication results, stratified by sex	Comparison population

This document is confidential.

Header	Table Number	Name	Analysis Set

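### SAP 7.1.6 can count one heart failure admission twice and adds deaths that endpoint #3 excludes; SAP 7.1.5 tests paired counts as if independent

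*SAP*

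**What the plan says.** **Counting rule.** SAP 7.1.6 takes HFH from the Hospitalization page. It takes emergency department and outpatient IV diuretic visits from the "AE page with AEs resulted in = 'Emergency Department (ED) visit'/'Hospitalization'/'Urgent, unscheduled outpatient office/ practice", for AEs categorised as heart failure. Each subject's total number of events goes into a Poisson model with a log-exposure offset. No de-duplication rule is given, and no other SAP section gives a CRF source for visits.

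**Definitions.** Protocol 14.6 puts HFH inside the heart failure AE category: "A HF Event includes hospitalization for HF and may include urgent, unscheduled outpatient office/practice or Emergency Department (ED) visits". It defines an urgent HF visit as an "urgent, unscheduled office/practice or ED visit for a primary diagnosis of HF but is not admitted to the hospital". Protocol 9.3.1 says of adverse events that they, "regardless of seriousness, severity, or presumed relationship to study therapy, must be recorded using medical terminology in the source document and in the eCRF". SAP 7.1 adds that "only hospitalizations due to heart failure and stay at least 24 h will be considered as HF related hospitalizations".

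**Deaths.** SAP 7.1.6 defines its rate as "The rate of mortality and HF hospitalizations or HF emergency department/hospital outpatient IV diuretic visits in each cohort" and gives the CRF source for deaths. SAP 3.3 words endpoint #3 as "Comparison of the number of HF Hospitalizations or Emergency Department/ Hospital Outpatient IV diuretic visits of Cohort #1 and Cohort #2 + #3". Table 14.2.2.3.1 is titled "Comparison of HF hospitalizations or HF emergency department/hospital outpatient IV diuretic visits of Cohort #1 and Cohort #2 + Cohort #3". Neither mentions mortality.

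**Pre/post comparison.** SAP 7.1.5 compares HFH per subject after implant with HFH per subject before implant by Wilcoxon rank sum tests at 6 and 12 months. It has no exposure term.

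**Correlation.** SAP 7.1.2 plans a negative binomial sensitivity analysis of the primary endpoint to capture within-subject correlation. SAP 7.1.6 has no such analysis.

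**The concern.** An HF admission is a heart failure AE that resulted in hospitalisation. Under the protocol's reporting rules it should appear on the AE page as well as on the Hospitalization page. Followed literally, 7.1.6 then counts it once as an HFH and again as a visit. The visit rule also conflicts with protocol 14.6, where an urgent visit excludes admission.

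SAP 7.1.8 (endpoint #5) and 7.1.9 (endpoint #6) add HFH and visits without a source rule of their own, so they inherit the double count if they use this one. SAP 7.1.12 has no HFH component and could only misclassify admissions as outpatient visits.

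Duplicated events come in pairs within a subject, which makes the Poisson standard error too small. Differences in risk between subjects have the same effect even without duplicates. In 7.1.5 the unpaired test ignores the link between a subject's two counts. Death and dropout shorten only the post-implant window, which produces an apparent reduction.

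**Working it through.** The plan states no power or event count for these endpoints, so there is no figure of its own to reproduce. All figures are for 6 months.

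**Inputs.** Assumed composite rate 0.34 (protocol 10.3). Death fractions from the protocol 10.3 table: 15/270 = 0.056; 107/1200 = 0.089; 16/234 = 0.068; and from a 12-month 0.089, 1 − exp(ln(1 − 0.089)/2) = 0.046. Range 0.046 to 0.089. Dropout about 10% (protocol 6.1). Visit rates, frailty variances and the 20% effect below are assumptions.

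**(a) Double count.**
- HFH per subject: H = 0.34 − 0.089 = 0.251 to 0.34 − 0.046 = 0.294.
- Extra events if every HFH is on both pages: 0.251 × 450 = 113 to 0.294 × 450 = 132; in 85 Cohort #1 subjects, 21 to 25.
- Inflation with V true visits per subject: (2H + V)/(H + V) = 2.0 at V = 0 and 1.5 at V = H. If half are duplicated, 1.5 and 1.25.
- With deaths D in the sum (7.1.6 as written, 7.1.8): (2H + V + D)/(H + V + D) = 1.74 to 1.87 at V = 0 and 1.43 to 1.46 at V = H.

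**Effect on the 7.1.6 test.** If a share f of HFH is duplicated, the mean is H(1 + f) + V and the variance is H(1 + 3f) + V. The dispersion φ is their ratio. A nominal one-sided 0.025 test then has size 1 − Φ(1.96/√φ). For f = 1: φ = 2 at V = 0, size 0.083; φ = 5/3 at V = H, size 0.065. SAP 7.1.6 states no alpha, so 0.025 is assumed. Simulation (85 vs 450 subjects, H = 0.25 or 0.29, V = 0 or H, gamma frailty, deaths left out, 20,000 replicates) gave:

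| HFH on both pages | No frailty | Frailty variance 0.5 to 2 |
|---|---|---|
| None | 0.026–0.030 | 0.036–0.094 |
| Half | 0.052–0.067 | 0.073–0.121 |
| All | 0.067–0.086 | 0.089–0.146 |

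De-duplication moves the test to the first row but leaves the frailty column. After de-duplication, a robust standard error gives 0.027–0.032 and a maximum likelihood negative binomial model 0.015–0.030. The latter rests on 600 replicates, with simulation error about √(0.025 × 0.975/600) = 0.006.

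**(b) Deaths.** The same fractions × 450 give 20 to 40 deaths.

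**(c) Pre/post test.** Simulation of 450 pairs with shared frailty variance 0.5 to 2, two-sided 0.05, 1,200 replicates:

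| | Mean 0.27 | Over means 0.27 to 1.0 |
|---|---|---|
| Rank-sum size | 2–4% | 0.1–4% |
| Rank-sum power, 20% reduction | 18–30% | 18–70% |
| Signed-rank power | 35–39% | 35–88% |
| Paired rate model power | 36–40% | 36–89% |

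At a 58% reduction every test has at least 99% power.

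10% dropout at uniform times removes about 0.10 × 0.5 = 5% of post-implant exposure; the simulated post/pre ratio with no true change was 0.950 to 0.958. Signed-rank then rejects 6–7% at mean 0.27 and up to 12% at mean 1.0. The paired model with offset rejects 4–6%.

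**The case against.** Several points on the other side have force.

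- **The double count is conditional.** The CRF is not available. The hospitalisation option may have been meant to catch HF admissions under 24 h, which fail the HFH definition. The rule carries no such restriction, however, so as written it also catches counted HFH. For the adjudicated repeats, nothing shows which counting rule applies.
- **Nothing decisive depends on it.** SAP 7.1.6 treats its p-values as exploratory in effect, SAP 2.4.2 makes other secondary p-values nominal, and no alpha is set. This limits the weight of the test-size figures. It does not excuse wrong event counts in prespecified tables.
- **The rank-sum test is less harmful than it looks.** Under 10% dropout and no true change it rejects 3.0–5.5% at mean 0.27 and 1.7–7.3% at means 0.4 to 1.0, because its conservatism largely offsets the exposure bias. Signed-rank does worse on this point, so it can only be supportive. The power loss is material only for modest effects: the 1-year pre/post reduction of 58% quoted in protocol 1.2 would be found by any of these tests.
- **Cohort #1 and death counts may be understated.** Using the protocol's control rates of 0.39 to 0.46 less the same death fractions, full duplication adds 0.301 × 85 = 26 to 0.414 × 85 = 35 events in Cohort #1. Over all 535 subjects in the Comparison Population, deaths would be about 24 to 48.
- **Deaths could be handled another way.** Retitling the tables or reporting deaths separately would also reconcile the text. Removal fits the endpoint as defined, and endpoint #5 already combines deaths with these events.

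**Conclusion.** The concern holds. The rule in 7.1.6 as written counts an HFH twice whenever it is on both pages, and it contradicts protocol 14.6. Its rate contains deaths that the endpoint, section heading and table titles leave out. The test in 7.1.5 is unpaired and unadjusted for exposure.

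The most important consequence is wrong counts: 1.5 to 2.0 times too high for HFH plus visits under full duplication, and 1.25 to 1.5 times under half, given 0 to 1 true visits per HFH. The Poisson variance fault in 7.1.6 is separate and remains after de-duplication if subjects differ in risk. The 7.1.5 fault mainly costs power for modest effects. The primary endpoint and the gated 12-month endpoint do not use the visit rule and are unaffected. These points should be corrected, but the trial's success criteria do not depend on them.

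**What to change.** 1. In 7.1.6, 7.1.8, 7.1.9 and their adjudicated repeats, delete the hospitalisation option from the visit rule and count each HF episode once. An HF AE linked to a counted HFH, including an ED visit that ends in admission, should not also be a visit.
2. State how HF admissions under 24 h are handled. They are neither an HFH (SAP 7.1) nor an urgent visit (protocol 14.6), and step 1 drops them unless they are assigned.
3. In 7.1.12, state that admitted events are not outpatient visits.
4. Remove mortality from the 7.1.6 rate.
5. Use a robust standard error or a negative binomial model in 7.1.6.
6. In 7.1.5, replace the rank-sum test with a paired rate model, for example Poisson GEE with robust standard error and log-exposure offset, with signed-rank as support only. State that this does not remove regression to the mean from selecting subjects on a prior HF event (inclusion criterion 5).

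The cost is SAP wording and some programming, with matching by subject and date if the CRF has no link field. Hospitalisations and visits are already listed separately (Listings 16.2.6.3 and 16.2.6.4). With only 85 subjects in Cohort #1, the robust test stays slightly above 0.025.

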1.2. Timings of Analyses

Main analysis will be performed after all Cohort #2- Previously enrolled Treatment Arm subjects and Cohort #3- Newly enrolled subjects completed the Month 6(V5) study visit or discontinued earlier. This main analysis will include all endpoints and analyses described in the SAP as far as data allow. The cleaning process will be completed at this stage, saying that the main analysis will be based on clean and coded data. Protocol deviations will be assessed and analysis sets will be defined following Syneos Health SOP (Blind) Data Review and Definition of Analysis Sets (3911) prior to the cut-off date for database (soft) lock. At this stage it will be decided if the analysis based on the Per-protocol population will be performed. Analysis will be performed on all analysis sets deemed relevant for the analysis. Listings will include all data collected until the cut-off date, by visit summaries will include data until V5 (Month 6), summaries (e.g. medication, or adverse events) without visit information will include all data until the cut-off date.

Additionally, an analysis on safety data will be performed once, the first 50 subjects which have been implanted with the Cordella PA Sensor have completed V4, Month 3 and also when 100 subjects have completed V3, Month 1. These safety analyses may occur at the same time depending on the timing of study visits. Analysis will be done on as much as possible clean and coded safety data.

The follow-up (final) analysis is planned after all subjects have completed the final study visit (V9, Year 3) or terminated early from the study.

An independent Data Safety Monitoring Board (DSMB) will review descriptive summaries of accumulating safety and subject disposition data on regular basis. Further description of the DSMB analyses can be found in the DSMB Statistical Analysis Plan Version 3.1 dated 07-Feb-2022 [1] and the DSMB charter Version 4.0 dated 04-Mar-2022 [1]. The study team from Syneos Health Biostatistics will perform the analyses.

The cut-off time point for the safety analysis and first two DSMB meetings expected to be identical. Outputs described in the DSMB SAP will cover the safety and DSMB analysis.

This document is confidential.

2. Study Objectives

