5.2. Key Definitions

Age

Age at screening is derived in the database and this value will be used for all analyses.

Definition of Baseline for safety assessments

Baseline will be defined as the last available value prior to the implant of Cordella PA Sensor and may be at any visit between Screening (V1) and Cordella PA Sensor Implant Visit (V2).

Definition of Baseline for PAP measurements

Baseline will be defined as value at Implant Visit (V2) obtained before discharge .

Change from Baseline

Absolute change from baseline:

Absolute change = Post-baseline value –baseline value

Time to Onset of AE

Time to onset of AE [days] = Date of start of AE – Date of implant of Cordella PA Sensor + 1

Start Day of concomitant medication

If medication starts before date of implant of Cordella PA Sensor:

Start Day of Medication = Date of start of medication – Date of implant of Cordella PA Sensor

If medication starts at/after date of implant of Cordella PA Sensor

Start Day of Medication = Date of start of medication – Date of implant of Cordella PA Sensor + 1

Incomplete start dates of medication will not be imputed. Start day of medication will be missing.

Stop Day of concomitant medication

If medication stopped before date of implant of Cordella PA Sensor:

Stop Day of Medication = Date of end of medication – Date of implant of Cordella PA Sensor

If medication stops at/after date of implant of Cordella PA Sensor

This document is confidential.

Stop Day of Medication = Date of end of medication – Date of implant of Cordella PA Sensor + 1
Incomplete end dates of medication will not be imputed. Stop day of medication will be missing.

Definition of study completed/discontinued/ongoing

A subject will be defined as study ‘completed’/‘discontinued’ based on the eCRF information. At the time of the pre-defined main analysis, subjects which are ongoing at date of cut-off will be counted as ‘ongoing’.

Time since first diagnosis of heart failure

Time since diagnosis [months] = ((Date of Screening – Date of first HF diagnosis)+1)/30

Exposure time:

which would be exact 6 or 12 months (180 or 365 days respective) post-implant visit for subjects who are still in the study at/after this timepoint.

which would be [date of last available date – date of Implant visit + 1] for subjects who withdraw from study prior to month 6 or 12 (180 or 365 days respective) post-implant visit.

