7.1.11. Days Alive and Out of Hospital (DAOH)

Days Alive and Out of Hospital (DAOH) calculated by subtracting days in hospital from total exposure time, where a subject's exposure is the time to death, early study discontinuation or 6 or 12 months, respectively, whichever is the smallest will be presented by means of descriptive statistics at 6 and 12 months post-implant visit.

Analysis will be done based on mITT population, PP population, and Cohort #1 population. Prior to the date of cut-off for the main analysis, it will be confirmed, if analysis based on PP population will be required.

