7.1.14. Change in PA pressure

Change from baseline in PAP parameters collected via CorPASS: pulmonary artery pressure systolic, pulmonary artery pressure diastolic, pulmonary artery pressure mean and pulse will be presented by treatment group by means of descriptive statistics at before and after 6-minute walk test.

mPAP will be summarized by 'Above target range', 'Within or below target range', and 'Overall' for subjects with a baseline mPAP, at all study visits as described in [Appendix 1: Time and Event Schedule](#) including post implant measurement, and sitting vs. supine measurements. Shifts in mPAP from baseline over all post-baseline visits will be presented. Target range of mPAP is 5-20 mmHg. When there are more than one available results collected on same visit, please use the earliest one.

Analysis will be done based on mITT population, and PP population. Prior to the date of cut-off for the main analysis, it will be confirmed, if analysis based on PP population will be required.

This document is confidential.

7.1.15. Percentage of device success as documented by ability of the System to successfully transmit PAP data

For the analysis of this endpoint, external data, provided by Endotronix, will be used. The provided data will include information if the missing PAP data are due to the System issues.

Following derived parameters will be presented:

- A) Total overall number of days of data collection, defined as the sum of all planned collection days (until end of study for final analysis or date of early discontinuation or date of cut-off or date of V6, Month 12 for the main analysis, whichever is smaller) of all subjects, excluding the days with missing data collection due to the subject's missing data transmission.
- B) Number of days with missing overall successful transmission of the collected data due to the System issues, defined as the sum of all unavailable days due to the System issues (until end of study for final analysis or date of early discontinuation or date of cut-off or date of V6, Month 12 date for the main analysis, whichever is smaller) of all subjects
- Overall device success rate of transmission (%), defined as $A-B/A * 100$
- Per subject device success rate will be calculated similar to the rules above, based on per subject data only.

Per subject device success rate will be presented by means of descriptive statistics, overall device success rate as percentage, other parameters will be presented using counts.

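### The exposure rule for the 12-month endpoints omits the data cut-off: read literally it credits 365 days to subjects observed for 6 to 12 months at the main analysis, and SAP 5.2 leaves those subjects undefined

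*SAP*

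**What the plan says.** SAP 1.2 triggers the main analysis when all Cohort #2 and #3 subjects have completed the Month 6 visit or discontinued, and adds: "This main analysis will include all endpoints and analyses described in the SAP as far as data allow".

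The exposure rule appears in several places:

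- SAP 7.1.6 (Cohort #1 against Cohorts #2+#3, at 6 and 12 months): "where a subject's exposure is the time to death, early study discontinuation or 6 or 12 months, whichever is smaller". The same section describes the rate as events "divided by the (total observed exposure time/180 or 365) in each cohort".
- SAP 7.1.11 (days alive and out of hospital, DAOH): "where a subject's exposure is the time to death, early study discontinuation or 6 or 12 months, respectively, whichever is the smallest".
- SAP 7.1.1 (primary endpoint) has the same minimum for 6 months. SAP 7.1.4 (first secondary endpoint, 12 months), 7.1.9 and 7.1.12 take their method from it.

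SAP 5.2 defines exposure in two branches. Exactly 180 or 365 days is given "for subjects who are still in the study at/after this timepoint". Time to the last available date is given "for subjects who withdraw from study prior to month 6 or 12 (180 or 365 days respective" days). The same section recognises a third group at the main analysis: "subjects which are ongoing at date of cut-off will be counted as" ongoing. That group has no exposure branch of its own.

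Elsewhere the SAP does stop the clock. SAP 7.1.15 (device success) uses "date of early discontinuation or date of cut-off or date of V6, Month 12 for the main analysis, whichever is smaller", and the time-to-event analyses in 7.1.9 and 7.1.10 censor at the last available date.

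**The concern.** At the main-analysis cut-off, subjects implanted in roughly the last six months of enrolment are alive, in the study and observed for about 180 to 364 days. They have neither a death date nor a discontinuation date, so the smallest term left in the 7.1.6 and 7.1.11 rule is 12 months. Their events are known only to the cut-off, but the denominator would run to day 365.

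On that reading the error has one direction: the 12-month rates come out too low. It affects the first secondary endpoint, which carries a performance goal and is tested after the primary for a labelling claim, and the 12-month parts of 7.1.6, 7.1.9 and 7.1.12. Cohort #1 was enrolled before the redesign amendment of November 2021 and should have passed 12 months by the cut-off. The understatement would therefore fall almost entirely on Cohorts #2+#3 and favour them in 7.1.6. For DAOH, days not yet observed would be scored as days alive and out of hospital.

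**Working it through.** **The plan's own figure.** SAP 2.4.2 states about 95% power for 0.55 against a goal of 0.70, one-sided 0.025, with 406 subjects followed for 12 months. With a Wald test on the log rate, z = ln(0.70/0.55) × √(406 × 0.55) − 1.96 = 0.241 × 14.94 − 1.96 = 1.64, which gives 95.0%. The exact Poisson test (reject at 251 events or fewer) gives 96.9%. The stated figure is reproduced, and it presumes 12 months of follow-up.

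**Size on the literal reading.** Let f be the share of Cohort #2+#3 subjects with under 365 days at the cut-off, and m their mean observed days. Ignoring deaths and dropouts, whose exposure is already right:

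relative understatement = f × (1 − m/365).

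If the cut-off is last implant + 180 days and follow-up is spread evenly over 180–365 days, m = 272.5 and the factor is 1 − 272.5/365 = 0.253.

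**Inputs.** From the documents: 450 subjects in Cohorts #2+#3 (protocol 6.1); first implant in Q4 2019 and last estimated for Q1 2023 (protocol 6.3). Assumed: the Cohort #2/#3 split, the shape of accrual, the length of Cohort #3 enrolment and the cut-off lag.

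Worked example: Cohort #2 = 85, and Cohort #3 = 365 accrued evenly over 14 months (14 × 30.4 = 425.6 days). The share of Cohort #3 in the last 185 days is 185/425.6 = 43.5%. Then f = 0.435 × 365/450 = 35.3%, and the understatement is 0.353 × 0.253 = 8.9%.

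| Assumed accrual | f | Understatement |
|---|---|---|
| All 450 evenly over 36–40 months | 15–17% | 3.9–4.3% |
| Cohort #2 of 50–150; Cohort #3 evenly over 12–16 months | 25–45% | 6.4–11.4% |
| Same, Cohort #3 accrual rising linearly (m somewhat lower) | 41–67% | 11.2–19.0% |
| Cohort #2 of 85, 14 months, cut-off 60 days later: even / rising | 24% / 41% | 4.1% / 7.4% |

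**What it does to the numbers.** A reading of 0.59, the first secondary endpoint's point-estimate limit, would correspond to a true rate of 0.59/0.96 = 0.61 at 4% and 0.59/0.81 = 0.73 at 19%. The prior-treatment mean of 0.64 and the goal of 0.70 both lie inside that span. With no true difference, the 12-month rate ratio of Cohorts #2+#3 to Cohort #1 would read 0.96 down to 0.81.

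If the formal 12-month test were run at this cut-off, with a true rate of 0.70 and N = 406:

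| Understatement | Confidence bound below 0.70 | And estimate below 0.59 |
|---|---|---|
| 0% | 2.4% | 0.3% |
| 4% | 9.7% | 2.0% |
| 8% | 27% | 8.6% |
| 15% | 74% | 45% |

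For DAOH, the most any one subject can be over-credited is 365 − 180 = 185 days.

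**Other readings of the same text.** Using time actually observed gives no understatement. A program that follows 5.2 to the letter could leave the offset missing for ongoing subjects under 12 months. The model would then drop them but keep late-implanted subjects who died or left, which pushes the rate upward. One data set can therefore give three different 12-month results.

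**The case against.** The strongest reply is that the SAP never intends to credit 365 days. SAP 5.2 gives full time only to subjects still in the study at or after the timepoint, and a subject at day 240 is not there yet. SAP 7.1.1 and 7.1.6 speak of observed exposure time, and 7.1.4 uses log follow-up time as the offset. This stands as evidence of intent, and it is why one cannot say that these subjects will be divided by 365. It does not close the gap: the operative sentence in 7.1.6 and 7.1.11 is a minimum with no cut-off term, and 5.2 supplies no value instead.

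Second, the size depends on accrual. This stands. A reader might infer a tighter band such as 8–15%, but that needs f between 0.08/0.253 = 32% and 0.15/0.253 = 59%, and nothing in the documents fixes f. The upper part of the 4–19% range rests on rising accrual, which is assumed.

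Third, a reader might infer that the formal 12-month test is compromised. The SAP does not say at which analysis that test is made. Its power statement supposes 12 months of follow-up, and SAP 2.2 refreshes the complete outputs at study end, when every subject has passed 12 months or left. The pass probabilities above are therefore conditional.

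Fourth, 7.1.6 treats its p-values as explanatory and DAOH is descriptive. That limits the consequence there but does not make those figures right.

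Finally, the explicit cut-off in 7.1.15 concerns planned collection days in external data. It shows that the authors had the term available, not that its absence elsewhere was an oversight.

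**Conclusion.** The point holds as a conflict between sections with a one-sided consequence on the literal reading. At the main analysis the 12-month exposure rule omits the cut-off, 5.2 assigns ongoing subjects under 12 months to neither branch, and the references to observed or follow-up time point to actual time. If the minimum is applied as written, the 12-month Cohort #2+#3 rates are understated by f × (1 − m/365). That is about 4–19% under the accrual, cohort split and cut-off lags assumed above, none of which the documents give. The exploratory 7.1.6 comparison would then favour Cohorts #2+#3, on the premise that Cohort #1 is fully observed at 12 months, and 12-month DAOH would include unobserved days.

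The 6-month primary endpoint is not affected beyond edge cases: the Month 6 visit may fall up to 14 days early, so a few late subjects could be credited with up to 14 unobserved days. The final analysis is not affected. The plan should be amended, but this does not threaten the primary conclusion.

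**What to change.** In SAP 5.2, 7.1.1, 7.1.4, 7.1.6 and 7.1.11, define exposure as the earliest of death, discontinuation, data cut-off and day 180 or 365, minus the implant date, plus 1, and count events only up to that date. SAP 7.1.9 and 7.1.12 then follow by reference.

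DAOH is summarised in days rather than as a rate, so shortening exposure would not make subjects comparable. For 12-month DAOH at the main analysis, include only subjects implanted at least 365 days before the cut-off, whatever their later status. State at which analysis the formal 12-month test is made.

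The cost is one added term in the definition and a smaller set for 12-month DAOH. Compared with the literal rule, the 12-month figures at the main analysis become slightly less favourable and less precise.
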